3.6.3 Vital Signs

Vital signs parameters include weight, height/length, systolic blood pressure, diastolic blood pressure, heart rate and body temperature (°C). Blood pressure and heart rate will be measured after the subject has been sitting for at least 5 minutes. Vital signs will be measured at Screening, Visit 2, Visit 3, Visit 4, Visit 5 and Visit 6. Additionally, vital signs will also be measured at the pre-assignment visit for the 1 month to < 2 years age group. At Visit 7, vital signs are measured if the subject has an ongoing AE that requires onsite assessment/management, or if the subject early discontinued.

Values and change from baseline will be summarised at each scheduled visit by parameter.

3.6.4 Physical Examinations

Physical examination parameters include an assessment of general appearance, skin, head, eyes, ears, nose and throat, cardiovascular, respiratory, abdominal, gastrointestinal and musculoskeletal systems. A physical examination will be performed at Screening and Visit 6. At Visit 7, those in the 2 years – 17 years age group will have a physical examination if the subject has an ongoing AE that requires onsite assessment/management, or if the subject early discontinued.

Values will be summarised at each scheduled visit.

All physical examinations data will be listed.

4 ANALYSIS TIMING

4.1 Interim Analysis

If less than 91 subjects in total have been randomised when 32 ferric maltol subjects have completed, then an interim analysis of the primary effectiveness endpoint (change in Hb concentration from baseline to Week 12) will be conducted. If significant, the study will stop recruitment. If not significant, the study will continue (all subjects will be assigned to ferric maltol) until 54 subjects have been recruited in the ferric maltol arm.

If an interim analysis is conducted, a Pocock spending function will be used. The interim analysis will be based on a (100-3.45)% two sided confidence interval. If the study does not stop after the interim analysis, the final analysis will be based on a (100-2.57)% two sided confidence interval.

4.2 Pre-Final Analysis

After the database is locked and exclusions from analysis populations have been finalised, the pre-final analysis will be generated. If the study does not stop after the interim analysis, the analysis will be based on a (100-2.57)% two sided confidence interval. Topline tables, figures and listings (TFLs) will be provided approximately 1 week after database lock and pre-final TFLs will be provided approximately 3 weeks after database lock.

4.3 Final Analysis

After all comments on the pre-final analysis have been resolved and the study database is declared final, the final analysis will be generated. Final TFLs will be provided approximately 1 week after the study database is declared final. If there were no changes to the pre-final analysis or the study database, the pre-final TFLs may be considered final. In addition to TFLs, SDTM (study data tabulation model) data and ADaM data along with associated files will be provided. Associated files may include: annotated CRFs, SDTM specifications, SDTM programs, ADaM specifications, ADaM programs, TFL programs, and CDISC (Clinical Data Interchange Standards Consortium) Define packages for both SDTM and ADaM data.

5 CHANGES FROM PROTOCOL-SPECIFIED STATISTICAL ANALYSES.

The primary analysis for change in Hb is based on mITT, and additional sensitivity analyses will be based on the ITT and PP population.

The addition of changes in iron markers from baseline to Week 4 as a secondary endpoint deviates from the secondary endpoints listed in section 6.4 of the protocol.

6 PROGRAMMING SPECIFICATIONS

Analyses will be performed using SAS® version 9.4 or higher. All available data will be presented in subject data listings which will be sorted by subject and visit date as applicable. Detailed Programming Specifications will be provided in a separate document.

APPENDIX A: REFERENCES

APPENDIX B: LABORATORY TESTS

Clinical Chemistry

Albumin Alanine Aminotransferase

Alkaline Phosphatase Amylase

Aspartate Aminotransferase Blood Urea Nitrogen

Calcium Chloride
Creatinine Folate
Gamma-glutamyl Transferase Glucose

Phosphorous Potassium

Sodium Total Bilirubin

Total Cholesterol Total Protein
Uric Acid Vitamin B12

Hematology

Absolute reticulocyte count Haemoglobin

Haematocrit Mean Cell Volume

Statistical Analysis Plan Version 2.0 / 10-Jul-2024

Red blood cell count Platelet count White blood cell count (total and differential (% and absolute)) Iron Markers **Ferritin** Serum Iron Transferrin **Total Iron Binding Capacity** Transferrin Saturation **Unsaturated Iron Binding Capacity** APPENDIX C: SAMPLE CODE Note: USUBJID = Unique subject identifier TREATMENT = Treatment VISIT = Visit BASE = Baseline value CHG = Change from Baseline ****************************** proc mixed; class USUBJID TREATMENT VISIT;

model CHG=TREATMENT BASE VISIT TREATMENT*VISIT / solution cl;

repeated VISIT / type=UN sub=USUBJID;

Ismeans VISIT*TREATMENT/cl diffs;

run;

Note: In case the model will not converge with the unstructured covariance structure, the heterogeneous compound symmetry (CSH) or the heterogeneous Toeplitz structure (TOEPH) will be used instead.

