2.2.4 Sample Size Determination

In total up to 110 patients will be recruited into the study. Up to 98 subjects will be randomised in the 2 -17 years cohort and up to 12 subjects will be assigned in the <2 years cohort.

The aim is to recruit up to 49 subjects in each treatment group in the 2 – 17 years cohort. At least 12 subjects in each age group respectively (i.e. 24 subjects in total) will be included in the PK analysis group in the ferric maltol oral suspension group. A sample size of 49 in the Ferric Maltol group provides at least 80% power to demonstrate that the lower bound of the 95% confidence interval for increase in Hb at 12 weeks, compared with baseline, is above zero. This assumed that the standard deviation (SD) of the change from baseline is 1.2 g/dL or lower and the true mean change is at least 0.5 g/dL.

Every effort will be made to recruit up to 12 subjects in the under 2's age group but in case of reasons of feasibility it cannot be completed, then the study may be completed without that cohort.

If less than 91 subjects in total have been randomised when 32 ferric maltol subjects have completed treatment (or withdrawn from the study), then an interim analysis of the primary effectiveness endpoint (change in Hb concentration from baseline to Week 12) will be conducted. If significant, the study will stop recruitment. If not significant, the study will continue (all subjects will be assigned to ferric maltol) until 54 subjects have been recruited in the ferric maltol arm.

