3.1.6 Handling of Dropouts and Missing Data

In general, missing data will not be imputed unless otherwise specified. Only observed data will be used in the summaries and analyses.

For adverse events (AEs) with incomplete or missing dates, imputation for start and stop dates relative to the start date of study drug is necessary to define an AE as treatment emergent. For missing AE start day, the 1st of the month will be used. If this day is before the day of study drug start and the end date of AE is on or after the date of first study drug, or if the AE end date is completely missing, the start date of study drug will be used. For missing start day and month, the start day and month will be January 1st. If January 1st is before start day and month of study drug, the start date of study drug will be used.

Partial dates for concomitant medications will be imputed to determine prior and concomitant status. Partial dates will be imputed as above for AEs. If the start date is completely missing, the start date will equal the date of first study drug. If the stop date is known and prior to the first date of study drug, the start date will equal the stop date of concomitant medication. If the stop date is completely missing, the concomitant medication will be considered as ongoing.

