3.4.1 Primary Endpoint Analysis

Primary Analysis

The change in Hb concentration from baseline to Week 12 will also be summarised based on the mITT Population for each treatment group using descriptive statistics summarised by mean, standard deviation, median, and range (minimum and maximum).

The efficacy of ferric maltol will be assessed via the change in Hb concentration from baseline to Week 12 using a mixed model for repeated measures (MMRM) approach. The analysis will include fixed effects for treatment, visit, and treatment-by-visit interaction, along with a covariate of the baseline value as a continuous covariate. In the MMRM model, both assigned and randomised ferric maltol subjects will be included in the ferric maltol arm. A separate analysis will be performed only including randomised subjects.

If no interim analysis is conducted then 95% CIs will be displayed. If an interim analysis is conducted and the study does not stop after the interim analysis, the final analysis will be based on a (100-2.57)% two sided confidence interval.

The MMRM analysis will be implemented using SAS® Proc Mixed. Example SAS code can be found in Appendix C.

Sensitivity Analysis

Change in Hb concentration from baseline to Week 12, will be summarised for subjects randomised/assigned when the endpoint was designated as secondary and for subjects randomised/assigned after the endpoint was changed to a primary endpoint.

Change in Hb concentration from baseline to Week 12 will also be assessed for the ITT and PP population.

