3.6.2 Clinical Laboratory Tests

Clinical Chemistry and Haematology will be collected at the Screening Visit and Visit 6 (Day 84). In addition, Haematology will be collected at Visit 4 (Day 28) for those subjects in the 2-17 years of age group. Additionally, Hematology and iron markers will be collected at Visit 2 for the 1 month to < 2 years age group.

At Visit 7, Clinical Chemistry and Haematology will be collected if the subject has an ongoing AE that requires onsite assessment/management, or if the subject early discontinued.

Chemistry parameters include vitamin B12, folate, alanine aminotransferase (ALT), aspartate aminotransferase (AST), alkaline phosphatase (ALP), gamma-glutamyl transpeptidase (GGT), total bilirubin, creatinine, amylase, blood urea nitrogen (BUN), phosphorous, sodium, potassium, chloride, calcium, total cholesterol, uric acid, glucose, total protein, albumin.

Haematology parameters include red blood cell count, haemoglobin, haematocrit, mean cell volume (MCV), white blood cell count (total and differential (% and absolute)), absolute reticulocyte count and platelet count.

Descriptive statistics for each safety laboratory parameter will be presented for baseline values and for values and the change from baseline at each post-baseline visit.

Values outside the normal range will be categorised as below the lower limit of normal or above the upper limit of normal based on the central laboratory's normal reference range. Values

outside of the normal range will be summarised. Shifts from baseline to worst post-baseline category will be tabulated by laboratory parameter and shift category (low to low, normal to low, high to low, low to normal, normal to normal, high to normal, low to high, normal to high or high to high) for chemistry and haematology parameters.

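### The primary MMRM assumes, without justification, one baseline-Hb slope for Week 4 and Week 12; if the slopes differ, the Week 12 estimate loses some precision and, with baseline-dependent dropout, is biased.

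*SAP*

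**What the plan says.** SAP 3.4.1 makes an MMRM the primary analysis of Hb change and states its mean model: "The analysis will include fixed effects for treatment, visit, and treatment-by-visit interaction, along with a covariate of the baseline value as a continuous covariate". The sample code in Appendix C agrees: "model CHG=TREATMENT BASE VISIT TREATMENT*VISIT / solution cl". Neither contains a baseline-by-visit term.

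The rest of the model is flexible by visit. The treatment effect has its own value at each visit, and the covariance is unstructured: "repeated VISIT / type=UN sub=USUBJID".

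Two scheduled post-baseline Hb visits feed the model. Day 84 applies to everyone. Day 28 applies to older children only: "In addition, Haematology will be collected at Visit 4 (Day 28) for those subjects in the 2-17 years of age group". Infants assigned to ferric maltol are included in that arm. SAP 3.1.6 sets the general missing-data rule: "Only observed data will be used in the summaries and analyses". The LSMEANS statement names no baseline value at which the means are evaluated.

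**The concern.** The slope of change on baseline at visit t equals Cov(Hb0, Hbt)/Var(Hb0) - 1. Equal slopes therefore require baseline Hb to covary equally with Week 4 Hb and with Week 12 Hb. If that covariance weakens as treatment corrects the anaemia, the Week 12 slope is steeper. This is plausible, but the documents neither show it nor rule it out. It is the one part of the mean model that is held constant over visits, and no reason is given.

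It matters because the MMRM is the primary analysis's only handling of missing Week 12 Hb. Its validity under missing at random depends on the mean model being right at Week 12. Infants have no scheduled Week 4 value, so their adjustment uses a slope estimated partly from other children's Week 4 data.

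**Working it through.** **Inputs from the documents.** Ferric maltol n = 49, SD of change 1.2 g/dL, true change 0.5 g/dL (SAP 2.2.4); up to 12 infants, all on ferric maltol; 1:1 allocation from age 2. No dropout rate is given for this trial. The protocol synopsis reports 87% completion in the adult IBD study, so 100 - 87 = 13% is the low scenario, with 25% as a high one.

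**Inputs assumed.** Baseline Hb SD 1.0 g/dL; Week 4 change with mean 0.3 and SD 0.9; residual correlation 0.6; half of dropouts without a Week 4 value; lower-baseline children dropping out more (odds ratio 2 or 4 per SD); infants with the same baseline distribution as older children; slope pairs as listed below.

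**Step 1: the plan's own figure.** SAP 2.2.4 states: "A sample size of 49 in the Ferric Maltol group provides at least 80% power". The SE is 1.2/√49 = 0.171, and 0.5/0.171 = 2.917. Power is Φ(2.917 - 1.960) = 83.1%, or 81.5% with the noncentral t. The stated figure reproduces.

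**Step 2: why bias needs two conditions.** Ignoring what Week 4 records add,

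bias ≈ (fitted common slope - true Week 12 slope) × (mean baseline of all subjects - mean baseline of those observed at Week 12).

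Equal slopes make the first factor zero. Dropout unrelated to baseline makes the second factor zero.

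**Step 3: large-sample bias.** A two-visit unstructured model was fitted to 200,000 simulated subjects per scenario. Entries are the ferric maltol Week 12 mean minus the truth, in g/dL. The mean is evaluated at the mean baseline of all subjects (subj.) or at the mean over analysed records (rec.).

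| Slopes Wk 4 / Wk 12 | Dropout, OR | One slope, subj. | `BASE*VISIT`, subj. | One slope, rec. | `BASE*VISIT`, rec. |
|---|---|---|---|---|---|
| -0.5/-0.5 | 13%, 2 | -0.004 | -0.004 | -0.034 | -0.034 |
| -0.5/-0.5 | 25%, 4 | 0.001 | 0.000 | -0.092 | -0.092 |
| -0.3/-0.5 | 13%, 2 | -0.014 | 0.001 | -0.035 | -0.030 |
| -0.3/-0.5 | 25%, 4 | -0.048 | -0.001 | -0.109 | -0.092 |
| -0.3/-0.7 | 13%, 2 | -0.029 | -0.001 | -0.056 | -0.046 |
| -0.3/-0.7 | 25%, 4 | -0.089 | 0.003 | -0.162 | -0.128 |
| -0.2/-0.8 | 13%, 2 | -0.037 | -0.004 | -0.064 | -0.052 |
| -0.2/-0.8 | 25%, 4 | -0.121 | -0.002 | -0.194 | -0.148 |

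With unequal slopes but dropout unrelated to baseline (OR 1), the one-slope bias stays within 0.005. Where both conditions hold, the subject-mean bias runs from -0.01 to -0.12 g/dL, which is 0.01/0.5 = 2% to 0.12/0.5 = 24% of the assumed change. The fitted common slope sits nearer the Week 4 value: for -0.3/-0.7 it is about -0.40 to -0.43.

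**Step 4: the reference baseline.** In the -0.3/-0.7, 25%, OR 4 row, moving from subject mean to record mean under `BASE*VISIT` changes the bias by -0.128 - 0.003 = -0.131. Dividing by the slope, -0.131/-0.70 = 0.187, so analysed records have a mean baseline about 0.19 g/dL above that of all subjects. The interaction does not touch this shift. At the record mean, with unequal slopes, `BASE*VISIT` leaves between 0.148/0.194 = 76% and 0.030/0.035 = 86% of the bias.

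**Step 5: precision at trial size.** 1,000 simulated trials per scenario: ferric maltol 49 + 12 infants without Week 4, ferrous sulfate 49; REML.

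| Slopes | SE, one slope / `BASE*VISIT` (13%, OR 2) | SE, one slope / `BASE*VISIT` (25%, OR 4) | Ratios, including 13% with OR 1 |
|---|---|---|---|
| -0.5/-0.5 | 0.1482 / 0.1484 | 0.1585 / 0.1591 | 0.996-0.998 |
| -0.3/-0.5 | 0.1494 / 0.1482 | 0.1602 / 0.1593 | 1.006-1.009 |
| -0.3/-0.7 | 0.1372 / 0.1327 | 0.1460 / 0.1412 | about 1.034 |
| -0.2/-0.8 | 0.1288 / 0.1214 | 0.1393 / 0.1301 | 1.06-1.07 |

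**The case against.** The best defence is that one common slope is a legitimate, parsimonious model and that every condition for harm is assumed. The documents give no baseline SD, no slopes, no dropout rate for this trial and no link between dropout and baseline Hb. At the mild end the bias is about 0.01 g/dL and the SE loss under 1%. The bias runs against the drug. SAP 3.4.1 also plans a separate analysis of randomised subjects only, which leaves the assigned infants out. All of this stands, and it makes the point conditional and modest. It does not justify the constraint, because dropping it costs almost nothing.

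Three stronger readings are tempting, and the documents do not support them.

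- **The estimate is biased whenever dropout depends on baseline Hb, and its SE is always too large.** Neither follows. With equal slopes the baseline term handles such dropout, and the planned SE is slightly smaller.
- **The code would use the wrong confidence level.** It has no ALPHA= option, so run unchanged it would print 95% limits. At a final look after an interim that did not stop the trial, that would give a simulated overall two-sided error of 6.8%, against 4.9% at the stated levels. But SAP 3.1.5, 3.4.1, 4.1 and 4.2 fix the level for that look, for example "the final analysis will be based on a (100-2.57)% two sided confidence interval", and 3.4.1 presents the code as an example only. This is a coding note.
- **The model should be limited to scheduled visits.** SAP 3.1.2 deliberately windows early-termination and unscheduled data into analysis visits, and removing Hb from dropouts would discard information that a missing-at-random analysis uses.

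**Conclusion.** The point holds in conditional form. The common slope is an unjustified restriction in the primary model. If the slopes differ, the Week 12 SE is about 0.6-7% larger over the slope pairs examined. If dropout also depends on baseline Hb, the Week 12 ferric maltol mean is off by about -0.01 to -0.12 g/dL. If the slopes are equal there is no such bias, and the planned model is 0.2-0.4% more precise.

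The sign rests on two assumptions: a steeper negative slope at Week 12, and more dropout among children with lower baseline Hb. The estimate is then pulled down, which costs accuracy and power but does not produce a false claim of an Hb increase. By the product in Step 2, reversing the dropout pattern would reverse the sign.

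The reference baseline is a linked weakness. If the software evaluates the least-squares means at the mean over analysed records (an assumption about its default), baseline-dependent dropout shifts the result under either model, even with equal slopes.

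**What to change.** In SAP 3.4.1, add a baseline-by-visit interaction to the listed effects, and state that the Week 12 least-squares means are evaluated at the mean baseline Hb of all mITT subjects. In Appendix C:

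`model CHG = TREATMENT BASE VISIT TREATMENT*VISIT BASE*VISIT / solution cl;`

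`lsmeans VISIT*TREATMENT / cl diffs at BASE=<mITT subject mean>;`

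Both parts are needed. If the software default is the record mean, the interaction alone leaves most of the bias.

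The cost is one extra parameter with the two scheduled Hb visits, and at most about 0.4% more SE if the slopes turn out equal. Any further analysis visit populated by windowed early-termination or unscheduled Hb adds one more parameter. The visit windows in SAP 3.1.2 can stay as they are.

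As a minor coding note, add ALPHA= to the LSMEANS statement at the level SAP 3.1.5 already requires: 0.05 with no interim, 0.0345 at the interim, 0.0257 at a final analysis after it.
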